2.1.6. Sample size

To achieve at least 80% power to detect a mean difference between groups of 10 points in patient's global health status/quality of life using an analysis of covariance (ANCOVA) adjusted for baseline global health status/quality of life, at the two-sided 2.5% significance level assuming a standard deviation of 25 points and a correlation of 0.3 between baseline and 24 weeks, a total sample size of 220 patients is needed with a balanced design (allocation ratio 1:1). Taking into account the partially nested study design (there is only a cluster effect of navigators in the intervention group), 115 patients in the control group and 131 patients in the intervention group is most efficient, assuming on average 1.5 patients per navigator in Belgium (Flanders), Ireland, Italy, the Netherlands, and Portugal (recruiting 5/6 of all patients), and 10 patients per navigator in Poland (recruiting 1/6 of all patients), and an intra-cluster correlation (ICC) of 0.10. Anticipating a drop-out rate equal to 50% (17.5% due to mortality, 32.5% due to other reasons),

229 subjects in the control group and 260 subjects in the intervention group are needed (total sample of 489, of which 81 patients from Poland and 83 patients from the other countries).

The sample size calculation was performed using SAS software (version 9.4) and is based on the paper from Moerbeek and Wong (2008).

The sample size calculation is based on the following assumptions:

- 1) A mean difference between groups of 10 points is considered the smallest clinically relevant difference in the mean score of EORTC QLQ-C30.
- 2) The standard deviation of 25 points reflects the heterogeneity in the score at 6 months in EORTC QLQ-C30 in a similar usual care population (EORTC Quality of Life Group, 2008).⁴⁴
- 3) An ICC of 0.1 was chosen as a conservative estimate as there is currently no empirical data to support an exact estimate of the ICC.
- 4) A correlation between baseline and 24 weeks in baseline global health status/quality of life of 0.3 was chosen as a conservative estimate considering that correlations for longitudinal measures are very rarely below 0.5.
- 5) A drop-out of 50% is a more conservative estimate than those reported in the Nav-Care feasibility and pilot studies (35% over 1 year²⁶, 40% over 1 year¹⁴, 17% over 6 months²⁷). Moreover, the final analysis will include the available information from patients who drop out.

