2.3. Data collection, management, and analysis

2.3.1 Data collection methods (for outcome and process evaluation)

Informed consent will be obtained either on a pen-and-paper form through in-person contact or by posting a form to the participant together with a post-stamped return envelope and asking them to mail it back to the research team (if in-person contact is not possible) (see Appendices 6 and 7 for information letters and informed consent documents). Participants who are neither able to meet the researcher in person, or send the informed consent form by mail will be given the option of informed consent by telephone, which will be audio recorded using encrypted devices with audio files stored securely, similar to procedures in an existing study that tested a range of remote options for enrollment and consent of older people into research studies. ⁵⁰ In case the participant is illiterate, the researcher will read the study information and consent form out loud to the participant. If they know how to sign, the participant will be asked to sign the informed consent form themselves, a witness will be asked to sign to confirm that the information has been read out loud to the participant and that he/she understood and agreed to take part.

After having obtained informed consent from both the older person and the close family caregiver (if present), the researcher/research assistant will perform baseline measurements. In case the first contact with the participants occurred by phone, the researcher/research assistant will make an appointment to meet with them in the older person's home (or other preferred location). After obtaining baseline measurements, the researcher will check to which intervention arm the older person (and family caregiver) is randomised (see 2.2.1) using RedCap and inform them to which group they are assigned. In case the older person and close family caregiver (if

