present) are randomised to the intervention group, the researcher/research assistant will inform them that they will be contacted by the navigator coordinator within one week. In case the patient and close family caregiver are randomised to the control group, the researcher/research assistant will tell them that they will be visited by the researcher after 12 weeks (approximately 3 months) and that they will be contacted by the navigator coordinator after 24 weeks (approximately 6 months). After each enrolment of a patient and family caregiver (if present), the researcher/research assistant will send the patient's contact details and group allocation to the navigator coordinator, who will then contact the patient and introduce the intervention at the appropriate time. As a visual aid, the researchers will give a leaflet to the participants with pictures of the different people involved in the study (i.e. researchers who will visit on a regular basis, intervention staff and names).

Data for primary, secondary, and tertiary or exploratory outcomes will be collected at baseline, at weeks 12, 24, 48 (and 72 in the control group) thereafter until the study end or until the patient's death (see figure under 2.1.6). For patients allocated to the intervention group, data collection will stop after 48 weeks; for those allocated to the control group, data collection will continue until 72 weeks after baseline. The researcher will try to perform the data collection with the patient (and their close family caregiver) within a timeframe of 1 week after each measurement time point.

Table 5 provides an overview of the measures used and information collected and the relevant time points for each throughout the study period. At each assessment point, the same measures will be administered, except for the collection of sociodemographic data that remain constant and that are collected at baseline only.

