Data collection will be through structured questionnaires during a face-to-face contact with the patient/family (at his/her preferred place). Questionnaires for patients will be administered by a researcher in a structured interview, and answers will be filled in by the researcher on a paper version of the questionnaire. Questionnaires for close family caregivers will be self-administered on paper (in the presence of the researcher if support is needed). Given that the questionnaire for close family caregiver contains questions that may be perceived as sensitive by the participants (e.g. on informal care burden), questionnaires for close family caregivers will preferably be administered in the absence of the older person with cancer (e.g. in a separate room).

If data collection during a face-to-face contact is not possible (e.g. because of COVID or other reasons) we will allow remote data collection as contingency (but not preferred) option, either through administration of the questionnaire through an online form or in a structured interview format through video call (e.g. Zoom). The mode of data collection will be determined by the researcher prior to each measurement in consultation with the patient and family caregiver. In case of remote data collection, some people may require support of a family carer or friend, and the researchers will encourage such support. The project consortium has ample experience in both face-to-face and remote (including online) data collection with older people in poor health, especially during the COVID-19 pandemic when this was the only way to obtain research data from patients. These methods were found to be acceptable and feasible and to provide high-quality data, given careful preparation of the data collection including identifying which participants needed support for remote data collection and ensuring they have it.

Each assessment will last around 45 minutes for patients and 30 minutes for family caregivers, but this will be tested during feasibility testing of measurements prior to the trial. This was shown to be an acceptable procedure and duration in previous trials with a similar population.⁵¹

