The inclusion and exclusion criteria are specified in the protocol. The number of ineligible persons with cancer randomized and the number of ineligible family caregivers included will be reported, together with reasons for ineligibility.

Recruitment

A CONSORT flow diagram will be used to summarize the number of persons with cancer who:

- gave informed consent
- were randomized
- received the allocated intervention
- did not receive the allocated intervention*
- lost to follow-up*
- discontinued the intervention*
- included in the primary analysis
- excluded from the primary analysis*

Withdrawal / Follow-up

Participants may withdraw from the intervention or from data collection. The PI can also discontinue a participant from the intervention in case of (1) significant study intervention non-adherence, (2) loss to follow-up, or (3) occurrence of an event, medical condition, or situation such that continued intervention would not be in the best interest of the participant. Reasons for discontinuing the intervention or data collection will be documented by the researcher/research assistant. In case participants only wish to withdraw from the intervention, they are invited to continue with data

^{*}reasons will be provided (e.g. withdrawal, death, etc).

collection, and priority will be given to collection of primary outcomes. Data collected after day of study withdrawal will not be used for analysis.

The numbers (with reasons) of withdrawals over the course of the trial will be summarized by treatment arm.

Baseline characteristics

Patient characteristics

- socio-demographic characteristics age, gender, country of birth, the country (ies) where the
 mother and father were born, highest educational level completed, whether the patient
 identifies with a specific religion or belief, with whom the patient currently lives,
 marital/partnership status, number of people that the patient consider to be important for
 them over the last 12 months and the extent to which the patient feels they can make ends
 meet (financial status).
- **clinical characteristics** organ or part of the body where the cancer was located and where it started, whether the cancer metastasized, age at diagnosis, comorbidities
- **functional status** Clinical Frailty Scale

Close family caregivers

socio-demographic characteristics – age (years), gender, country of birth, country(ies) where
the mother and father were born, highest educational level completed, whether the family

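### Outcome collection allows no telephone interview and no general primary-only assessment, so some frail patients risk an avoidable missing week-24 score

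*Combined protocol and SAP*

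**What the plan says.** **Mode.** Protocol section 2.3.1 sets the default: "Data collection will be through structured questionnaires during a face-to-face contact with the patient/family (at his/her preferred place"). The patient questionnaire is read out by a researcher as a structured interview. If face-to-face contact is not possible, remote collection is a permitted but not preferred fallback, "either through administration of the questionnaire through an online form or in a structured interview format through video call (e.g. Zoom"). On the choice of mode: "The mode of data collection will be determined by the researcher prior to each measurement in consultation with the patient and family caregiver". On help with remote collection: "some people may require support of a family carer or friend, and the researchers will encourage such support".

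**Telephone elsewhere.** Telephone contact is accepted for eligibility screening (sections 2.1.7 and 3.3) and for contact between navigator and patient (section 2.1.3; SAP, Interventions). Section 2.3.1 also accepts it for consent: participants who can neither meet the researcher nor post the form "will be given the option of informed consent by telephone", with an audio recording.

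**Content.** Section 2.3.1 states: "At each assessment point, the same measures will be administered", apart from sociodemographic data, which are collected once. It puts an assessment at about 45 minutes for patients. The SAP (Withdrawal / Follow-up) adds that for participants who withdraw only from the intervention and continue data collection, "priority will be given to collection of primary outcomes". No reduced assessment is described for anyone else.

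**Planned loss.** Section 2.1.6: "Anticipating a drop-out rate equal to 50% (17.5% due to mortality, 32.5% due to other reasons").

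**The concern.** Patients are 70 or over and meet a Clinical Frailty Scale criterion. Those without a close family caregiver are eligible, and recruitment deliberately seeks people who live alone, have small networks or have difficulty reading (section 2.1.7). Both permitted remote modes need equipment and internet, and the offered remedy is help from a carer or friend. A patient too unwell for a visit, with neither internet nor helper, could often still answer a short set of questions read out by telephone. The plan does not provide for that.

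What is at stake is the week-24 score itself. The primary model (SAP, Analysis methods) uses only baseline and week 24, so a week-12 score cannot stand in for a missing one. The main analysis assumes that missingness may depend on allocation, baseline outcome and country, but not on other values (SAP, Missing outcome data). Losses caused by deteriorating health strain that assumption. Section 2.3.1 lists burden and being too ill among the reasons for stopping data collection or the intervention.

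**Working it through.** **1. The passages side by side**

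- Remote outcome modes named: online form and video call. Telephone is not named.
- Primary items: 2 (EORTC QLQ-C30 global health/QoL) + 19 (MOS Social Support Survey, Table 5) = 21.
- Primary-first rule: applies on withdrawal from the intervention. Control patients start the intervention only after week 24, so before the primary endpoint they have none to withdraw from.
- Partial answers: any question may be refused (section 2.4.2). Global health/QoL is scored with at least 50% of items (1 of 2). Other scales need 70% (0.70 × 19 = 13.3, so 14 of the 19 MOS items). Skipping therefore protects a primary score only if enough primary items are reached.

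**2. Reproducing the plan's sample size** (inputs from section 2.1.6: difference 10, SD 25, correlation 0.3, two-sided alpha 2.5%, power 80%)

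- ANCOVA SD = 25 × √(1 − 0.3²) = 23.85.
- n per arm = 2 × (2.241 + 0.842)² × 23.85² / 10² = 108.1, so 109 per arm, total 218. With the noncentral t distribution, 110 per arm gives 80.2% power, total 220, as stated.
- Partial nesting with ICC 0.10: design effects in the intervention arm are 1 + 0.5 × 0.10 = 1.05 (1.5 patients per navigator, 5/6 of patients) and 1 + 9 × 0.10 = 1.90 (10 per navigator, Poland, 1/6). At 115 + 131 = 246, power is 81% with simple pooling and 82% with stratum weighting.
- Inflation for 50% loss: 115/0.5 + 131/0.5 = 230 + 262 = 492, against the stated 229 + 260 = 489. This agrees within rounding.

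**3. Size of the planned non-death loss**

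0.325 × 489 = 158.9, about 159 patients.

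**4. Illustration of recovery**

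The recoverable share f is an assumption; the documents give no figure. Total loss = 17.5% + 32.5% × (1 − f). Power uses the model in step 2, starting from 489 enrolled.

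| f | Scores regained | Total loss | Power |
|---|---|---|---|
| 0 | 0 | 50.0% | 81-82% |
| 10% | 16 | 46.8% | 84-85% |
| 20% | 32 | 43.5% | 86-87% |
| 30% | 48 | 40.3% | 88-89% |

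Check at f = 0 with simple pooling: 114.6 control and 129.9 intervention patients give a standard error of 3.20. Then 10/3.20 = 3.12, 3.12 − 2.24 = 0.88, and Φ(0.88) = 81%.

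The table applies to global health/QoL only, because the plan gives no planning inputs for MOS. It assumes that regained patients have the same effect, SD and correlation as the others and are spread over both arms in proportion.

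**The case against.** The case against is substantial.

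- **Existing flexibility.** Face-to-face contact may be anywhere the patient prefers, the mode is agreed before each measurement, and help with remote collection is encouraged. Patients may skip questions, and scales are scored from partial data. A reader might infer that only home visits count, that the full interview is all-or-nothing, or that patients without internet have no way to give a score. The documents support none of these. Repeating the same measures at each time point does not mean that every item must be answered.
- **Unknown size.** The group that would benefit cannot have a visit, cannot manage supported online or video collection, yet would answer by telephone. It may be small. The stated reasons for stopping (burden, lack of time, illness) cover intervention sessions as well as data collection, and none mentions mode.
- **No power deficit.** The 50% loss is a deliberately cautious allowance, above the earlier Nav-Care studies (one had 17% over 6 months), and enrolment already absorbs it. A reader might infer that the trial is underpowered; step 2 shows that it is not.
- **Missing data are examined.** The SAP plans added covariates (age category, functional status), jump-to-reference, tipping-point and survivor analyses.
- **Unseen detail.** Item order is in the questionnaire appendix and procedures are in a Quality Assurance Manual, neither of which is in the documents reviewed. Primary items may already come first.

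All of this limits the size of the point. It does not remove it. The sensitivity analyses show how far conclusions depend on missing scores but recover none. Help from a carer or friend is least available to the isolated patients whom recruitment seeks. Limiting modes could be defended as restricting measurement variation, but the plan already accepts two remote modes and gives no reason for omitting telephone for an interview that is already read out.

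**Conclusion.** The point holds as a cheap improvement. The plan names no telephone mode for outcomes and no general primary-only assessment, and its one primary-first rule does not reach control patients before week 24. Some avoidable non-death loss at week 24 is therefore a risk of unknown size within the planned 32.5%.

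The gain of 16 to 48 scores and the rise in power to about 84-89% depend on an assumed recovery of 10 to 30%. They illustrate scale and are not a forecast. They measure precision only. Any reduction in bias is plausible, because these losses probably relate to health, but it is not quantified. It would go too far to say that these patients will be missing, or that the sample size is in error.

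**What to change.** 1. In protocol section 2.3.1, add a researcher-led telephone interview to the permitted remote modes.
2. State that, in either arm, a patient who cannot or will not complete the full interview at week 24 is offered a minimum set: the 2 global health/QoL items and the 19 MOS items, given first. The target is week 24, because a week-12 minimum set would add nothing to the primary model.
3. Carry the same rule into the SAP (Withdrawal / Follow-up), so that priority for primary outcomes no longer depends on leaving the intervention.
4. Record mode and set in REDCap and report both by arm. Treat any analysis restricted to face-to-face assessments as supportive, because mode is chosen after randomisation and relates to health.

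**Cost.** A short protocol amendment with ethics approval, using the same staff and instruments. There will be slightly more mode variation, and secondary and exploratory measures will be missing for patients who give only the minimum set.

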2.3.2 Data collection methods process evaluation

The process evaluation includes two phases: development phase (before intervention delivery) and evaluation phase (during and after intervention delivery). In the development phase, the original Canadian Nav-Care intervention (Nav-Care©) will be adapted to the European context, and further adapted to country and cultural-specific contexts by Local Adaptation Teams (LAT) of each country (see protocol in appendix 1). A report per country will be written, potential barriers and facilitators will be mapped, and the intervention will be pilot tested (see earlier). In the evaluation phase, the quality and quantity of the delivered intervention will be measured, and the role of context will be analysed, using CFIR³⁶ and RE-AIM³⁷, two well-establised implementation science frameworks.

Short surveys for coordinators and navigators will be filled in shortly before the intervention starts, and at the end of the intervention period. During the intervention, the coordinators and trainers will keep diaries of their work, and navigators will fill in a short report of each client visit. After the intervention, each country will organize (group) interviews with navigators, coordinators, patients and family caregivers, and professionals involved in the recruitment and referral of patients. About 3-5 respondents per stakeholder group per participating setting in each country. The (group) interviews will be guided by topic lists based on CFIR and RE-AIM constructs.

For CFIR construct 'innovation', the Local Adaptation Team of each country will write a country report (development phase) and will fill in a short survey after the intervention (evaluation phase) (part of WP2, see protocol in appendix 1).

For CFIR construct 'outer setting' a researcher and trainer of each participating country will be interviewed by researchers of WP2, using a topic list (development phase and evaluation phase).

For CFIR construct 'inner setting' researchers of each country will interview the coordinator(s) and manager of each participating organization within their country, using a topic list (development phase and evaluation phase).

For CFIR construct 'characteristics of individuals' the coordinators, navigators and trainers of each participating country will fill in a short survey about confidence in taking their role (directly after their training and evaluation phase).

For CFIR construct 'Process' and 'RE-AIM dimensions (all evaluation phase):

- professionals involved in the recruitment and referral of patients will get a short survey every 2 months about referral and recruitment. (reach).
- trainers will keep a diary of all their activities, keep attendance lists of trainees (navigators and coordinators), and at the end of the trials an international group interview with trainers of each country will be held. (adoption)
- coordinators and trainers will keep diaries of their work, and navigators will fill in reports of each client visit during the intervention period. After the intervention, (group) interviews will be held with coordinators, navigators, patient/family carers. (implementation)
- coordinators, navigators, patients and family and professionals involved in the recruitment and referral of patients will be interviewed after the intervention. (implementation, maintenance)

Furthermore, information about RE-AIM dimensions will also come from data collection for the other CFIR constructs (see above).

Table 6 below provides a more detailed overview of what information will be collected, from which respondents, in which phase of the project. See appendix 8 for all data collection materials for the process evaluation and the informed consent documents.

Table 6 Overview measurements per group, measurement moment and what is measured

| Target population | Before intervention | During intervention | After intervention | CFIR/RE-AIM domains |
|---|--|-------------------------------------|--|--------------------------------------|
| Local Adaptation Team | Country report about adaptation + short survey with specific questions about intervention characteristics | | Short survey about evaluation intervention characteristics | CFIR: innovation, -, |
| Participating organizations (Manager + coordinator) | Interview about inner setting (barriers, facilitators) | | Interview about evaluation inner setting and intervention (barriers and facilitators - greatest success, greatest barrier) | CFIR: inner setting |
| | | | | |
| Coordinators | Short survey characteristics | Diary about process and recruitment | Short survey characteristics | CFIR: individual- characteristics |

| | individual | | individual | |
|---|---|--|--|--|
| | | | (group) interview about experiences (barriers, facilitators, adaptations) | RE-AIM: reach implementation, maintenance |
| | | | | |
| Navigators | Short survey characteristics Individual | Visit reports | Short survey characteristics individual | CFIR: individual-characteristics |
| | | | (group) interview about experiences (barriers, facilitators, adaptations) | RE-AIM: implementation, maintenance |
| | | | | |
| Trainers | Diary about process / trainer after each training/mentoring session | Diary about process / trainer after each training/mentoring session | Group interview with all international trainers about experiences | RE-AIM: adoption, implementation maintenance |
| | | | | |
| Professionals involved in the recruitment and referral of patients | Involved in LAT for feasibility check intervention | Short survey every 2 months about recruitment | Interview /short survey about evaluation intervention characteristics and recruitment/referral | CFIR: innovation RE-AIM: reach, maintenance |
| | | | | |
| Patients/family | | questions about experiences in WP3 survey | Interview about experiences | RE-AIM: implementation |

